Version B	10 FEB 2017	Changed Painful Peripheral Diabetic Neuropathy to Diabetic Peripheral Neuropathy to allow for a broad symptomatology to be included. Added information to how many times VPT test will be conducted to obtain the average value at each time point. Added additional primary endpoint to capture changes in both large and small nerve fiber responses. Updated response assessment from VPT change to change in 1-point decrease in NPRS over the last 24 hours. Added additional instruction and a visual for collecting the foot measurement, updated introduction and background section, and added additional medications to "allowed medications" section. Removed EQ-5D questionnaire and replaced with Neuro-QoL questionnaires.
Version C	22 FEB 2017	Change testing of plantar aspect to dorsal aspect for QST heat and cold testing. Updated Exclusion #3 added a timeframe of within 6 months of the Screening Visit and an upper limit of 1.4 for the ABI.
Version D	27 MAR 2017	Removed Summary of Diabetes Self Care Activities Questionnaire (SDSCA) to reduce patient fatigue with answering questionnaires. Switched NeuroQoL questionnaire with a single neuropathy-and foot ulcer-specific quality of life instrument.
Version E	19MAY2017	Updated locations for biopsies to be taken as well as the central lab used in analyzing the samples.
Version F	12JUN2017	Increase the number of sites from 2 to 4. Update Inclusion/Exclusion criteria to allow for a broader population to be enrolled. Allow all patients to voluntarily consent to biopsies.

Study Title Protocol Number Name of Study Device Phase of Development Objective	AMulti-Center,Sham-Controlled,Double-BlindRandomized Withdrawal Study of Pulsed ElectromagneticField (PEMF) Therapy to Evaluate Vibration PerceptionThreshold and Thermal Sensory in Subjects with DiabeticPeripheral Neuropathy in the Lower ExtremityRBI.2017.001PROVANT® Therapy SystemProof of ConceptTo demonstrate the effectiveness of PEMF treatment compared
	to sham treatment in changing Vibration Perception Threshold (VPT) and Thermal Sensory (QST) in patients with diabetic peripheral neuropathy (DPN) when treatment is administered twice daily through 120-day period.
Number of Subjects	Up to 40 subjects randomized 1:1.

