Adverse events will be mapped to preferred terms and body systems using the Medical Dictionary for Regulatory Activities (MedDRA) coding dictionary. While the primary presentation of adverse events will be subject-based, the number of adverse events will also be reported. The number and percentage of subjects reporting each event will be summarized during the treatment period by treatment assignment. Incidence of adverse events by maximum reported severity will also be tabulated. Serious adverse events and adverse events leading to discontinuation will be displayed.

D. Eligibility Criteria

Eligibility for participation in this study will be based on the inclusion/exclusion criteria. An individual subject may only be included in the study once.

1. Inclusion Criteria

- 1. Subject age is greater than or equal to 22 years and less than 80 years of age.
- 2. Subject has documented Type 1 or Type 2 diabetes mellitus (receiving insulin, diet controlled, or taking parenteral hypoglycemic agents)
- 3. Subject is on a stable antidiabetic regimen (medication and/or diet) to control their diabetes for at least 30 days prior to Screening.
- 4. Subject has an HbA1c <10% at Screening or within 2 months of Screening.
- 5. Subject has daily pain attributed to bilateral symmetrical Diabetic Peripheral Neuropathy with numbness, tingling, and/or burning based on clinical judgement for at least 6 months prior to screening.
- 6. Subject's pain or discomfort from DPN is identifiable.

- 7. Subject is in pain Phase 2, 3, or 4 as per the Phasing of Neuropathy Scale.
- Subjects average pain over the last 24 hours is ≥3 based on the 11-point Numeric Pain Rating Scale (NPRS) at the Screening Visit.
- 9. Subject has adequate lower extremity pulse in both feet and no intermittent claudication.
- 10. Subject is able to ambulate independently with assistive devices, but not wheel chair bound.
- 11. Subject is willing and able to give written informed consent and to comply with all parts of the study protocol.
- 12. Female subjects must be post-menopausal, surgically sterile, abstinent, or practicing (or agrees to practice) an effective method of birth control if they are sexually active for the duration of the study (Effective methods of birth control include prescription hormonal contraceptives, intrauterine devices, double-barrier methods, and/or male partner sterilization).

2. Exclusion Criteria

- 1. Subject is in pain Phase 1 or 5 as per the Phasing of Neuropathy Scale.

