- 2. Subject has an active, open ulcer on the lower extremities.
- 3. Subject has peripheral vascular disease defined as absence of more than one foot pulse per foot and/or ABI <0.8 and >1.4 and/or history of angioplasty or peripheral bypass surgery within 6 months of the Screening Visit.
- 4. Subject has venous insufficiency as classified by the Venous Insufficiency Classification System of grade C6.
- 5. Subject has undergone nerve decompression surgery on the lower extremities.
- 6. Subject has a history of previous kidney, pancreas, cardiac transplantation, or severe renal disease.
- 7. Subject has been diagnosed with non-diabetic chronic inflammatory neuropathic disease (e.g. end stage renal disease, hepatitis C, chemotherapy induced neuropathy, known connective tissue disease, systemic lupus).
- 8. Subject has peripheral vascular disease requiring revascularization of lower limb or amputation or evidence of ulcer amputation.

- 9. Subject has clinically significant cardiovascular disease within 6 months prior to screening (unstable or poorly controlled hypertension, transient ischemic attack, MI, unstable angina, arrhythmia, any heart surgery, stent placement, heart disease).
- 10. Subject has a history of any uncontrolled medical illness that in the Investigators judgment places the subject at unacceptable risk for receipt of PEMF therapy.
- 11. Subject requires or anticipates the need for surgery of any type or travel during the treatment period.
- 12. Subject has a total foot depth (most inferior aspect of the medial malleolus to the plantar aspect of the foot when residing on a treatment pad) of >8 cm.
- 13. Subject has received any investigational drug or device within 30 days prior to the Screening Visit or within 6 weeks prior to the Screening Visit for long acting lidocaine injection products.
- 14. Subject has used systemic corticosteroids within 3 months of the Screening Visit.
- 15. Subject has a history of malignancy within the past 5 years other than successfully treated non-metastatic basal cell or squamous cell carcinomas of the skin in the treatment area and/or localized in situ carcinoma of the cervix.
- 16. Subject has a serious psychosocial co-morbidity.
- 17. Subject has a history of drug or alcohol abuse, as confirmed by urine drug screen, within one year prior to the Screening Visit.

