Measurement of Ankle-Brachial Index (ABI): Subject is in a supine position, with the arms and legs at the same level as the heart for a minimum of 10 minutes before measurement to obtain the ABI measurement. ABI will be measured at the Screening Visit and the end of study visit (Day 121) on both legs. At Day 121, for those subjects who will have biopsies performed, ABI will be completed prior. The change from baseline will be captured and assessed.

Measurement of Foot Thickness: The depth of the foot (H) will be measured from the most inferior aspect of the medial malleolus to the plantar aspect of the foot when residing

on the treatment pad (see diagram below). The depth should not be more than 8cm for inclusion in the trial.

Hemoglobin A1c (HbA1c) Test: provides the average level of glucose in the blood over the past 2 to 3 months. For this test, the A1C Now[®] System will be used, subjects will have a finger stick to collect 5μ L of blood to obtain the A1c value at the Screening Visit to obtain eligibility (and baseline). At the end of the study visit (Day 121) the A1c will be collected and compared to the baseline value. Each subject will have a A1C Now[®] System assigned to them. The change from baseline will be captured and assessed.

Blood Glucose: measures the amount of sugar in the blood at the time of collection. A TRUE METRIX[®] PRO Professional Monitoring Blood Glucose System will be assigned to each subject for the course of the study. Subjects will have a finger stick to collect 5μ L of blood to measure their glucose value at the Enrollment Visit and on Days 30, 61, 91, and 121. The American Diabetes Association's goals for blood glucose control in patients with diabetes is 70 to 130 mg/dL before meals and less than 180mg/dL after meals.

Subject adherence: compliance with twice daily treatment with the study device will be assessed verbally during the Day 3 telephone call, at the interim visits and upon completion of the study. At each of the interim visits, subjects will be required to bring in their devices to ensure compliance by recording the usage meter reading on the side of the study device control panel.

Treatment Satisfaction: will be obtained at Days 15, 30, 45, 61, 75, 91, 105, and end of study visit to assess the patients level of satisfaction with the treatment. Once subjects are

randomized, they will also be asked which device (active of sham) they believe they were randomized to at Day 121 (blinding assessment).

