This is a proof of concept study with no formal hypothesis testing planned and therefore there is no power associated with this study. The sample size of 40 patients is a sample of convenience for this study.

VII. INFORMED CONSENT

It is the responsibility of the investigator, or a person designated by the investigator (if acceptable by local regulations), to obtain written informed consent from each individual participating in this study after adequate explanation of the aims, methods, objectives and potential hazards of the study. It must also be explained to the subjects that they are completely free to refuse to enter the study or

to withdraw from it at any time for any reason. Appropriate IRB-approved forms for obtaining written informed consent will be provided by the investigator or by Regenesis Biomedical, Inc. or their designee.

If new safety information results in significant changes in the risk/benefit assessment, the consent form will be reviewed and updated if necessary. All subjects (including those already being treated) will be informed of the new information, given a copy of the revised form and be re-consented to continue in the study.

VIII. INSTITUTIONAL REVIEW BOARD

This protocol, the informed consent form and any accompanying material provided to the subject (such as subject information sheets or descriptions of the study used to obtain informed consent) as well as any advertising or compensation given to the subject, will be submitted by the investigator or investigator's designee to an IRB. Approval from the IRB must be obtained before starting the study and should be documented in a letter to the investigator specifying the date on which the IRB met and granted the approval.

IX. TERMINATION OF THE INVESTIGATION

As the study sponsor, Regenesis Biomedical, Inc. reserves the right to terminate the study at any time. Should early termination be necessary, Regenesis Biomedical, Inc. and the investigator will consult and make sure that adequate consideration is given to the protection of subjects' interests.

Additionally, all clinical investigational data will be reviewed by the sponsor on a regular basis. Reports of all data will be made available to the Institutional Review Boards and to the FDA as required. Unanticipated adverse device events will be evaluated and reported in accordance with 21 CFR Part 812 requirements and as required by the governing IRB.

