- 6. Finally, divide the ankle pressure by the brachial artery pressure; the result is the ABI.

Obtained from: http://emedicine.medscape.com/article/1839449-overview#aw2aab6b4

Brachial Systolic Pressure

Anterior Tibial and Posterior Tibial Systolic Pressures

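### Exclusion 3 joins its two ABI limits with 'and', which no single ABI value can satisfy, so read literally the protocol's only ABI screen has no effect

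*Combined protocol and SAP*

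**What the plan says.** Exclusion 3 in Section III.D.2 defines peripheral vascular disease through three clauses: "absence of more than one foot pulse per foot and/or ABI <0.8 and >1.4 and/or history of angioplasty or peripheral bypass surgery". The sentence ends by limiting the procedure history to 6 months around the Screening Visit.

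The other passages that bear on it are:

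- **Which legs are measured.** Section III.L.4 states that "ABI will be measured at the Screening Visit and the end of study visit (Day 121) on both legs". Exclusion 3 names no leg.
- **What an ABI is.** The last step of Appendix D reads "divide the ankle pressure by the brachial artery pressure; the result is the ABI". It is one ratio per extremity.
- **Where 1.4 came from.** The Version C entry in the version history reads "Updated Exclusion #3 added a timeframe of within 6 months of the Screening Visit and an upper limit of 1.4 for the ABI". It is used here only as evidence of intent; the defect is in the current text.
- **Other arterial screens.** Inclusion 9 requires that "Subject has adequate lower extremity pulse in both feet and no intermittent claudication". Exclusion 8 covers disease that currently needs revascularization or amputation.
- **Screens on the source of pain.** Inclusion 5 requires daily pain attributed to diabetic neuropathy. Exclusion 22 removes subjects with other pain that would confuse its assessment.

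**The concern.** The two ABI limits sit at opposite ends of a range, yet they are joined by a bare 'and'. The same sentence joins its separate clauses with 'and/or', so the change of connective invites a literal, joint reading. On that reading the clause is idle. A subject whose screening ABI is abnormal, but who passes every other vascular criterion, is eligible as written.

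Three features of this trial make that worth correcting:

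- Skin perfusion pressure is a secondary endpoint, and a fall in pain score decides who is randomized. Section I says that ischemia may or may not add to leg pain in these patients, and it describes calcification of larger vessels.
- Consenting subjects have a punch biopsy at the distal leg. Appendix E already treats poor healing after biopsy as a reason to exclude some subjects with venous disease.
- Section IV.M asks sites to follow the protocol strictly. A site that enrols a subject with an ABI of 0.7 on the literal wording has not deviated from it. A site that excludes the same subject on this clause alone is relying on a reading that the text does not state. With up to 4 sites, both can happen.

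**Working it through.** The documents give no calculated figure on this point, so there is nothing to reproduce. The check is one of logic, with a count to show what each reading does.

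**Inputs.** Limits 0.8 and 1.4 (Exclusion 3); one ABI per leg (Appendix D); two legs measured (Section III.L.4). Assumption: ABI values run from 0.30 to 2.00 in steps of 0.01, giving (2.00 − 0.30)/0.01 + 1 = 171 values. This range is for illustration only. The empty result below holds for any range.

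**Step 1: partition of the values**

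- Below 0.8 (0.30 to 0.79): 50 values
- From 0.8 to 1.4 inclusive: 61 values
- Above 1.4 (1.41 to 2.00): 60 values
- Check: 50 + 61 + 60 = 171

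**Step 2: one ABI value under each reading**

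| Reading | Values that meet the exclusion |
|---|---|
| <0.8 *and* >1.4 | 0 of 171 |
| <0.8 *or* >1.4 | 50 + 60 = 110 of 171 |

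**Step 3: two legs per subject.** There are 171 × 171 = 29,241 pairs of leg values.

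| Reading | Pairs that meet the exclusion |
|---|---|
| 'And' within a leg | 0 |
| 'And' across legs (one leg <0.8, the other >1.4) | 2 × 50 × 60 = 6,000 |
| 'Or', any leg outside the limits | 29,241 − 61 × 61 = 25,520 |

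These are counts of grid points. They are not patient proportions.

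The cross-leg reading is not empty, but it needs opposite abnormalities in the two legs. It misses a subject with 0.7 in one leg and 0.9 in the other, and a subject with 1.5 in both.

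**Step 4: which leg.** Take a right-leg ABI of 0.9 and a left-leg ABI of 0.7. Even with 'or', this subject is excluded if either leg counts and eligible if only the right leg counts. The text does not settle it. Both feet are treated, while the sensory, conduction and perfusion measurements and the biopsies are on the right side (Sections III.L.1 to III.L.3).

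**Step 5: what else would catch the subject.**

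- The pulse clause needs more than one absent pulse in a foot. Appendix D names two pulse sites there, dorsalis pedis and posterior tibial; on those two, both must be absent.
- Inclusion 9 relies on an adequate pulse, which is not defined, and on the absence of claudication.
- The procedure clause reaches back only 6 months.
- Exclusion 8 needs disease that requires intervention, or evidence of an ulcer amputation.
- Exclusion 2 needs an open ulcer, and Exclusion 22 needs confusing pain.

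A subject with adequate pulses, no claudication, no recent procedure, no ulcer and no confusing pain, but an ABI outside the limits, passes all of these.

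**The case against.** The strongest reply is that the intent is plain. The version history calls 1.4 an upper limit, and an investigator who meets an impossible condition would most naturally read the two figures as alternatives. That stands, and it makes this a drafting error rather than a deliberate design choice. It does not remove the need to correct an operative eligibility rule, because each site is left to repair the sentence for itself.

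A reader might go further and infer that the clause excludes nobody, so that subjects with arterial disease can enter freely. The documents do not support that. The clause is strictly empty only for a single ABI value, since a cross-leg reading is possible. The other criteria listed above also continue to screen for arterial disease and for pain from other sources.

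A reader might also see a conflict between Exclusion 3, with its 6-month window, and Exclusion 8, which has no window: "Subject has peripheral vascular disease requiring revascularization of lower limb or amputation or evidence of ulcer amputation". The two address different things. Exclusion 3 concerns a procedure already done, and Exclusion 8 concerns disease that now requires one. Exclusion criteria are cumulative, so passing one and failing another is ordinary. A subject revascularized 2 years ago with no present need passes both on a natural reading.

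Finally, the harm cannot be sized. Skin perfusion pressure is analysed as change from baseline, biopsies are voluntary, and Section VI.E says "This is a proof of concept study with no formal hypothesis testing planned and therefore there is no power associated with this study". All of this is fair. No power or error-rate figure is affected, and the point rests on the wording of the criterion, not on an estimated bias.

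**Conclusion.** The point holds as a wording defect in an operative criterion. As written, 0 single ABI values can meet the ABI clause of Exclusion 3, and no other eligibility criterion uses an ABI value. The practical gap is narrow: a subject whose only abnormality is a low or high ABI, plus possible inconsistency between up to 4 sites and over which leg counts.

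The number of subjects affected, out of up to 40, is unknown because the documents give no ABI distribution. That sites would in fact differ is a possibility, not something the documents show.

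The conclusion assumes only that the criterion is applied to each leg's ratio as worded. That the two limits were meant as separate bounds rests on the version history.

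**What to change.** Reword the ABI clause of Exclusion 3 so that the two limits already stated are alternatives, that is 'or' in place of 'and', in line with the intent recorded for Version C. In the same amendment, the sponsor should state which leg's screening ABI decides eligibility. The documents do not settle this, so the choice is the sponsor's. Exclusion 8 needs no change on this account.

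The cost is a short protocol amendment and notice to sites. No procedure is added, because ABI is already taken on both legs at Screening. The downside is possibly a few more screen failures at any site that had been applying the literal wording.

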- 18. Subject has an implanted pacemaker, defibrillator, neurostimulator, spinal cord stimulator, bone stimulator, cochlear implant, or other implanted device with an implanted metal lead(s).
- 19. Subject is currently pregnant or planning on becoming pregnant prior to Day 121.
- 20. Subject has previously treated with PROVANT[®] Therapy System within 60 days on the lower extremity.
- 21. Subject is unwilling or unable to follow study instructions or comply with the treatment regimen, diary documentation, and study visits.
- 22. Subject has pain from any other source that can confuse the assessment of the pain associated with DPN.
- 23. Subject has a clinically significant foot deformity (Charcot's syndrome or club foot).

- 24. Subject has received nerve blocks for neuropathic pain within 4 weeks of the Screening Visit.
- 25. Subject has been diagnosed with mononeuropathy.
- 26. Subject has a skin condition that could alter their sensation.
- 27. Subject has had a previous surgery to the spine or lower extremity with residual symptoms of pain or difficulty with movement.
- 28. Subject has moderate or severe arthropathy (RA, OA, Gout) that causes discomfort during casual walking or stair climbing.

E. Recruitment

Recruitment for study subjects will be drawn from the patient population at the investigative study site. Recruitment efforts will be supplemented with IRB approved internet, radio and/or print advertising as necessary.

F. Randomization

The schedule for randomization of subjects and allocation to treatment will be prepared using SAS[®] (Statistical Analysis System; Cary, NC) to create a computer-generated scheme based on a permuted block algorithm. The randomization schedule will randomize in a 1:1 ratio (active : sham) to a device based on the randomization kit numbers. The kit numbers will be assigned sequentially to subjects that qualify for inclusion into the study.

G. Device Description

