APPENDIX E – GRADING SYSTEM FOR VENOUS INSUFFICIENCY

VENOUS INSUFFICIENCY CLASSIFICATION SYSTEM (CEAP)

For the initial assessment of a patient with venous insufficiency, the clinical severity is established by observation (without any specialized testing). The classification system increases in severity from C0-C6 as noted below.

Patients with C3-6 disease demonstrate an increasing severity of chronic venous insufficiency with chronic irreversible functional abnormality of the venous system. Patients with foot edema that typically resolves overnight is generally classified as a C2 (as long as they do not also meet criterion for C5 or C6). Patients with persistent ankle edema, gaiter lipodermatosclerosis, and history of a healed ulcer or current open ulcer will be excluded from the trial as a consequence of their increased risk of developing a chronic non-healing venous ulcer after biopsy.

Grade	Description
C 0	No evidence of venous disease.
C 1	Superficial spider veins (reticular veins) only
C 2	Simple varicose veins only
C 3	Ankle edema of venous origin (not foot edema)
C 4	Skin pigmentation in the gaiter area (lipodermatosclerosis)
C 5	A healed venous ulcer
C 6	An open venous ulcer

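### Exclusion 4 bars only venous grade C6, while Appendix E excludes a wider group for ulcer risk after biopsy, and no biopsy step checks venous grade

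*Combined protocol and SAP*

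**What the plan says.** Section III.D ties entry to its lists of criteria: "Eligibility for participation in this study will be based on the inclusion/exclusion criteria". Two exclusions bear on venous ulcers. Exclusion 2 reads "Subject has an active, open ulcer on the lower extremities". Exclusion 4 reads "Subject has venous insufficiency as classified by the Venous Insufficiency Classification System of grade C6".

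Appendix E holds the grading system that Exclusion 4 relies on, running from C0 to C6. C3 is ankle edema of venous origin, C4 is gaiter skin change (lipodermatosclerosis), C5 is a healed venous ulcer and C6 is an open one. Above the table, the appendix gives its own exclusion rule: "Patients with persistent ankle edema, gaiter lipodermatosclerosis, and history of a healed ulcer or current open ulcer will be excluded from the trial". The stated reason is their "increased risk of developing a chronic non-healing venous ulcer after biopsy".

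The biopsies are exploratory and voluntary (III.L.3). Each consenting subject has one punch at the right distal leg and one at the right distal thigh at Enrollment, and a second pair beside the first at the end of study. IV.B item 13 selects on consent, with a minimum of 2 subjects per pain phase. IV.K item 15 selects those who had a baseline biopsy.

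**The concern.** A site that opens Appendix E to apply Exclusion 4 finds a different exclusion rule there. A site that works only from III.D does not see it. The second site could, without breaking any listed criterion, enrol someone whom the appendix says must be kept out, and then take an elective punch from the lower leg of that subject twice.

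The hazard is the sponsor's own statement, not one brought in from outside. The only safeguard the protocol states against it is exclusion, and the listed criterion does not carry that exclusion. What is at stake is the safety of a possibly small group within an optional procedure.

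**Working it through.** No arithmetic decides this point. The check sets the two rules side by side by grade. The Appendix E sentence joins its signs with *and*, so it is read both ways.

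| Grade | Exclusion 4 | Appendix E, strict reading (all signs together) | Appendix E, list reading (any one sign) |
|---|---|---|---|
| C0 to C2 | admits | admits | admits |
| C3, ankle edema | admits | admits | excludes if persistent |
| C4, lipodermatosclerosis | admits | admits | excludes |
| C5, healed ulcer | admits | excludes if edema and lipodermatosclerosis are also present | excludes |
| C6, open ulcer | excludes | excludes if edema and lipodermatosclerosis are also present | excludes |

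**Step 1: is there a gap on every reading?** Yes. On the strict reading, the ulcer sign may be healed or open, so a C5 subject with the other two signs is excluded by Appendix E and admitted by Exclusion 4. On the list reading, the gap is C3 (persistent edema), C4 and C5.

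**Step 2: which reading is likelier?** The list reading, by inference. The signs follow rows C3, C4, C5 and C6 in order. The appendix also sets transient foot swelling apart ("Patients with foot edema that typically resolves overnight is generally classified as a C2"), which fits a rule that starts at C3. The strict reading would, taken alone, not exclude an open venous ulcer without the other signs. Against a full match, the C3 row says only "Ankle edema of venous origin (not foot edema" and does not require persistence.

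**Step 3: does another criterion close the gap?** No.
- Exclusion 2 covers open ulcers, so it overlaps C6 and does not reach C3 to C5.
- Exclusions 3 and 8 concern peripheral vascular disease, defined by pulses, ABI, revascularization or amputation.
- Exclusion 10 concerns risk from PEMF therapy, not from biopsy.
- Exclusion 22 (confusing pain from another source) might remove some painful venous disease.
- Exclusion 26, "Subject has a skin condition that could alter their sensation", might catch some C4 subjects at the investigator's discretion.
- Nothing in III.D names C3 or C5.

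**Step 4: does a biopsy step close it?** No. III.L.3 and IV.B item 13 use consent and pain phase; IV.K item 15 uses the prior biopsy. At Day 121 the protocol says explicitly that ABI and SPP come before the biopsy. The venous assessment is listed earlier in IV.K (item 3), but no text makes the biopsy depend on its result.

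**Step 5: what can be counted?** The minimum number biopsied is 2 per pain phase × 3 phases = 6. Punches per biopsied subject are 2 sites × 2 visits = 4, of which 1 × 2 = 2 are at the distal leg. The 6 is a count of everyone biopsied, not of subjects at risk. The documents give no distribution of venous grade, so the number at risk cannot be derived.

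**The case against.** The best case for the plan has four parts.

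First, grading a subject under Exclusion 4 requires Appendix E, so the site should meet the wider rule on the same page, and IV.M requires strict adherence to the whole protocol. The likelier outcome may be a query to the sponsor rather than a biopsy. This lowers the chance of harm but does not reconcile the texts, since III.D is where eligibility is decided.

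Second, C6 alone may be deliberate. The version history says Version F broadened the entry criteria and let all patients consent to biopsy. A reader might infer that this amendment loosened Exclusion 4 and left the appendix behind. The documents do not say which criteria changed. Even if it is so, Appendix E then needs correcting, and the group it names as at risk has become eligible for biopsy without a check.

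Third, a reader might infer that Appendix E plainly excludes every C3 to C6 subject. It does not say so: that extent rests on the list reading, and even then the edema must be persistent. This part of the objection stands, and it limits what can be called certain.

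Fourth, the biopsy is voluntary and exploratory, and the affected number could be zero. That stands too, and it keeps the severity at moderate. The consent pages are not in the reviewed text, so any biopsy warning there cannot be weighed.

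**Conclusion.** The conflict is in the current text and holds on any reading. What is certain is that C5 subjects who also have ankle edema and lipodermatosclerosis are excluded by Appendix E and admitted by Exclusion 4. What is probable, if the sentence is a list of signs, is a gap covering C3 with persistent edema, C4 and C5. No other criterion and no biopsy step closes either gap.

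The size is unknown. It would be wrong to offer the number of biopsied subjects as the number exposed. A reader might also infer a threat to the trial's results; nothing supports that, because the hazard named in Appendix E arises from the exploratory biopsy and no primary or secondary endpoint depends on it. This is a moderate subject-safety inconsistency, worth correcting before further biopsies are taken.

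**What to change.** The sponsor should state which grades are meant and make Exclusion 4 and Appendix E agree.

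**Default.** Keep C6 as the enrolment exclusion and correct Appendix E to say so. Bar from biopsy any subject with persistent ankle edema (C3), lipodermatosclerosis (C4) or a healed venous ulcer (C5), any one being enough. Write this into III.L.3 and IV.B item 13, using the Screening grade, and into IV.K item 15, using a venous assessment done before any end-of-study biopsy. State that the check also covers Day 91 non-responders and early withdrawals. IV.I sends the former to the Day 121 procedures and section V asks for efforts to do the same for the latter, while Appendix A footnote 3 can be read as limiting the venous assessment to responders who finish treatment.

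The cost is a short amendment and a notice to sites. Venous grade is already assessed at Screening and listed for Day 121, so no new procedure is needed. The downside is a smaller biopsy pool against the minimum of 2 per pain phase.

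**Alternative.** If Appendix E reflects the intended entry rule, widen Exclusion 4 to match it and state whether one sign is enough and whether C3 edema must be persistent. The effect on enrolment cannot be derived from the documents. It must be weighed against the minimum of 10 subjects in each of three pain phases, which is 10 × 3 = 30 of the up to 40 planned.
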